4.2. Inclusion Criteria

To be eligible for registry enrolment, patients must meet all of the following criteria:

- Age ≤ 17 years at time of administration of the first dose of etanercept
- Diagnosis of plaque psoriasis by a dermatologist
- Prior to enrolment, a clinical decision has been made to prescribe etanercept for the treatment of psoriasis
- Newly prescribed with initial etanercept or actively being treated with etanercept, regardless of length of treatment prior to study enrolment
- Capable and willing to provide paediatric assent, or written informed consent when applicable, and
- Parent(s)/legal representative of patient is capable and willing to provide written informed consent

- Evidence of a personally signed and dated informed consent document indicating that the patient (or a legally acceptable representative) has been informed of all pertinent aspects of the study must exist.

Please note: Currently etanercept is approved for the treatment of severe plaque psoriasis in children and adolescents from the age of 6 years who are inadequately controlled by, or are intolerant to, other systemic therapies or phototherapies. The registry protocol will not encourage use of etanercept at younger ages. However if a doctor, in collaboration with the child's parents, makes the independent clinical decision to prescribe etanercept to a child less than 6 years of age for severe plaque psoriasis, that child may be included in the registry.

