5. STUDY TREATMENT AND DURATION

There will be no dispensing of any study medication or protocol-specified procedures associated with participation in this registry. All medical treatment, including medications, is solely at the discretion of the treating physician in accordance with their usual care.

The total duration of the registry is approximately 9 years, including approximately 4 to 5 years for patient enrolment and 4 to 5 additional years for follow-up on all enrolled patients. Dermatologists will enrol eligible patients who are current users of etanercept at any time after they initiate such treatment for plaque psoriasis. The Sponsor expects to enrol the first patient in Q4 2010, with all follow-up to be completed in 2018. Follow-up will occur every 3 months during the first 2 years of the study and every 6 months thereafter (year 3 through the end of participation). Each patient is expected to participate for 5 years, or until the registry is completed in 2018, whichever comes first.

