9. ADVERSE EVENT REPORTING AND SERIOUS ADVERSE EVENT REPORTING

ADVERSE EVENTS

All observed or volunteered adverse events regardless of treatment group (if applicable) or suspected causal relationship to etanercept will be recorded on the adverse event page(s) of the case report form (CRF) as follows.

For all adverse events, the investigator must pursue and obtain information adequate both to determine the outcome of the adverse event and to assess whether it meets the criteria for classification as a serious adverse event (see section "Serious Adverse Events") requiring immediate notification to Pfizer or a Pfizer-designated representative. For all adverse events, sufficient information should be obtained by the investigator to determine the causality of the adverse event. The investigator is required to assess causality. For adverse events with a causal relationship to etanercept, follow-up by the investigator is required until the event or its sequels resolve or stabilize at a level acceptable to the investigator, and Pfizer concurs with that assessment.

All AEs must be evaluated by the site and assessed for seriousness, as defined below in [Section 9.1](#).

REPORTING PERIOD

All reportable serious and non-serious AEs directly observed or reported by the patient or caregiver to the physician or other site personnel, from the time of enrolment (i.e., informed consent has been obtained and the patient has received at least one dose of etanercept) through patient discontinuation from the registry, end of the observation period, or 28 days after the last dose of etanercept, whichever is later, will be assessed and recorded, if applicable, within the CRF. If a patient was administered etanercept on the last day of the observation period, then the reporting period should be extended for 28 calendar days following the end of observation. The site will record the diagnosis, if available. If no diagnosis is available, the site will be instructed to record each sign and symptom as an individual event.

If the investigator becomes aware of a SAE occurring at any time after completion of the study and s/he considers the SAE to be related to etanercept, the SAE also must be reported to Pfizer Safety.

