### **5.3 Definition and measurement of exposure/risk windows**

#### **5.3.1 Etanercept**

##### **TREATMENT PERIODS (INITIAL AND SUBSEQUENT)**

It is anticipated that the etanercept treatment status for each patient will change throughout follow-up. A standard course of etanercept treatment is expected to last up to 24 weeks. Patients successfully responding to the first etanercept treatment course may be exposed to subsequent treatment (i.e., when patients experience a disease flare) and time window between 2 (or more) consecutive courses of treatment may vary substantially.

For the initial course of etanercept, whether the patient completed 24 weeks of treatment is recorded (yes/no), and if no, the number of weeks of treatment will be reported. Completion of initial 24 weeks of etanercept is defined as starting the first dose of etanercept within 30 day before the enrolment date or any time after enrolment date, and continuing for at least 168 days.

For each subsequent treatment period of etanercept, start and stop dates of treatment are collected. For all subsequent periods, the duration of treatment in weeks will be calculated. Cumulative exposure will be calculated by the sum, for each etanercept treatment period, of: [last dose date – first dose date] + 28. If there are less than 28 days between treatment periods, exposure will be considered uninterrupted (i.e., part of the same treatment period).

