##### **CURRENT/RECENT TREATMENT VERSUS PAST TREATMENT**

In order to interpret reported events, time at risk of occurrence is established based on current or recent (within 28 days) exposure and past exposure.

**Past exposure** is defined as any exposure to etanercept, at any dose, with no reported exposure within the last 28 days.

**Current/recent exposure** is defined as on active etanercept treatment at the time of the event, or last dose of treatment within 28 days (inclusive) preceding the event.

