#### **6.5 Planned subgroups**

Descriptive analyses will be stratified, where specified, by:

- Enrollment type: Prospective (i.e., patients who started etanercept within 30 days before the enrollment date or any time after enrollment date) or retrospective
- Treatment period (initial 24 weeks/post 24 weeks/all follow-up)
- Completion of initial 24 weeks of etanercept exposure (yes/no/unknown)

Analysis of outcomes of interest:

- Etanercept exposure status (current/recent or past)
- Infection status (none during follow-up/in association with recent or current exposure/in association with past exposure)

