## PURPOSE SAP

### Protocol # B1801035

- The follow-up time for patients who had malignancies will be censored at the diagnosis date for each type of malignancy. The follow-up time after diagnosis of a malignancy will not be included in the calculation of time at risk or not at risk for the same type of malignancy. However, patients who reported a malignancy are still at risk of having a different type of malignancy. Malignancy types include but are not limited to: Solid malignant tumors, Non-melanoma skin cancers, Malignant tumors of hemopoietic and lymphoid tissues, Carcinoma in-situ.
- Time at risk (in years; for the current/recent etanercept-treated group only) of serious or pre-specified opportunistic infection (excluding malignancies) and other SAEs (excluding serious or pre-specified opportunistic infection and malignancies), respectively: cumulative period of etanercept exposure defined as the sum of each etanercept treatment period,  $[\text{date of last dose} - \text{date of first dose} + 1 + 28]/365.25$ .
- Time not at risk (this applies to time in years accrued after discontinuation of etanercept while followed in the registry, and excludes malignancies) of serious or pre-specified opportunistic infection and other SAEs, respectively: cumulative period without current/recent use of etanercept  $\{[(\text{date of study discontinuation}) - (\text{date of last dose} + 28) + 1] + [\text{intervals between treatment periods} > 28 \text{ days}]\}/365.25$ . For analysis purposes, time not at risk is the total study follow-up time minus the time at risk, which is defined above.
- Incidence rate is calculated as the number of individual events observed during the time at risk, divided by the total number of patient-years at risk for the event, multiplied by 100. Please note that the time at risk for malignancy will be censored at the diagnosis date of that specific malignancy.

In the example below, all person-time in blue would contribute to the ‘current/recent’ category, while all person-time in yellow would contribute to the ‘past treatment’ category for the assessment of SAEs and serious or opportunistic infections. Patients would be considered at risk of malignancies in both the blue and yellow periods.

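### The SAP obtains past-treatment time by subtracting from total follow-up, which misallocates person-time whenever enrolment and first dose fall on different dates, in opposite directions depending on which comes first

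*SAP*

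**What the plan says.** **Time not at risk.** SAP 6.6 gives three descriptions in one bullet. The scope is "this applies to time in years accrued after discontinuation of etanercept while followed in the registry". An explicit formula then covers the time after the last dose plus 28 days, and the intervals between treatment periods. The operative sentence follows: "For analysis purposes, time not at risk is the total study follow-up time minus the time at risk, which is defined above". Time at risk runs from first to last dose of each treatment period, plus 28 days. SAP 7.3 uses the two totals as the person-time for current/recent and past treatment in the incidence rate ratio.

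**Past exposure.** SAP 5.3.1 defines it as "any exposure to etanercept, at any dose, with no reported exposure within the last 28 days", so some earlier dose is required.

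**Enrolment relative to first dose.** The documents differ:

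- Protocol 9 (Reporting Period) counts events "from the time of enrolment (i.e., informed consent has been obtained and the patient has received at least one dose of etanercept" has been met, so enrolment follows the first dose.
- Protocol 5 agrees: "Dermatologists will enrol eligible patients who are current users of etanercept at any time after they initiate such treatment for plaque psoriasis".
- Protocol 4.2 admits patients "Newly prescribed with initial etanercept or actively being treated with etanercept, regardless of length of treatment prior to study enrolment", so a prescription is enough.
- SAP 5.3.1 defines completion of the initial 24 weeks as "starting the first dose of etanercept within 30 day before the enrolment date or any time after enrolment date" and continuing from there. SAP 6.5 defines prospective patients in the same way: "patients who started etanercept within 30 days before the enrollment date or any time after enrollment date".
- SAP 6.4 restricts the analysis population to enrolled patients with a documented dose. That condition would be redundant if enrolment already required one.

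**The concern.** A newly prescribed child may consent and have the baseline visit before the first injection. If follow-up starts at enrolment, the waiting time is not current/recent exposure, so the subtraction leaves it in the past-treatment denominator although the child has never been exposed. An event in that interval fits neither exposure class in SAP 5.3.1, so time is counted with no defined place for its events. The past-treatment rate falls and the rate ratio rises.

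A child already on etanercept at enrolment meets the reverse problem. Time at risk is counted from the first dose, before enrolment, and is subtracted from follow-up that begins later. Past time comes out too short, the past-treatment rate rises and the rate ratio falls.

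Infection risk during current or recent treatment is the first registry objective, and Protocol 7.6 names this within-registry contrast as the available comparison for infections. The SAP 7.3 rate ratio needs at least 5 infections in each group. The incidence rate stratified by exposure type has no such threshold and is affected in any case.

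**Working it through.** The plan states no person-time total, so there is no figure to reproduce. The check compares the SAP's rules day by day.

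**Inputs from the documents.** Follow-up is 5 years (Protocol 5), taken as 1,826 days. A course is 24 weeks, or 168 days (SAP 5.3.1). The risk tail is 28 days (SAP 6.6). The recruitment target is 60 to 80 (SAP 4), with 70 used here.

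**Assumptions.** The gap between enrolment and first dose is not given. A 1,400-day treatment duration stands for the long continuous use that the note in SAP 5.2.5 anticipates.

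**Formulas for one course.** Let E = enrolment, F = first dose, L = last dose and D = study discontinuation.

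- Time at risk = L − F + 1 + 28
- Subtraction rule = (D − E + 1) − (L − F + 29) = D − (L + 28) + (F − E)
- Past time under SAP 5.3.1 = D − (L + 28)
- Error of the subtraction rule = F − E days: positive if the first dose follows enrolment, negative if it precedes it
- Explicit formula in SAP 6.6 = D − (L + 28) + 1, which overlaps time at risk by one day

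**Results, in days per patient.**

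| Treatment | First dose relative to enrolment | Past time (5.3.1) | Subtraction | Ratio |
|---|---|---|---|---|
| 168 | 14 after | 1,616 | 1,630 | 1.009 |
| 168 | 30 after | 1,600 | 1,630 | 1.019 |
| 168 | 90 after | 1,540 | 1,630 | 1.058 |
| 168 | 30 before | 1,660 | 1,630 | 0.982 |
| 1,400 | 14 after | 384 | 398 | 1.036 |
| 1,400 | 30 after | 368 | 398 | 1.082 |
| 1,400 | 90 after | 308 | 398 | 1.292 |
| 1,400 | 30 before | 428 | 398 | 0.930 |
| 1,400 | 180 before | 578 | 398 | 0.689 |

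The last column is the factor by which the error in past time multiplies the rate ratio. For early starters the current/recent denominator is affected too. With a start 30 days before enrolment, 30 of the 196 days at risk precede enrolment. SAP 4 limits primary analyses to events during participation, so that denominator is overstated by 196/166 = 1.18, which lowers the ratio further.

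**Registry level, all inputs assumed.** Suppose 40 patients wait 2 to 8 weeks: 40 × 2/52.18 = 1.53 and 40 × 8/52.18 = 6.13 patient-years of never-exposed time. With 150 or 80 patient-years of true past time, the rate ratio is multiplied by 151.53/150 = 1.010 or 86.13/80 = 1.077. In the other direction, 20 patients with 16 weeks of prior treatment remove 20 × 16/52.18 = 6.13 patient-years, which cancels the larger figure.

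**Against the SAP's own interval.** Take 70 patients, all enrolled 30 days before the first dose, with 5 infections in each group.

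- 168 days of treatment: current/recent time is 37.6 patient-years, and past time is 306.6 correct against 312.4 by subtraction. The rate ratio is 8.16 (1.88 to 35.5) against 8.32 (1.91 to 36.1).
- 1,400 days: current/recent time is 273.7 patient-years, and past time is 70.5 against 76.3. The rate ratio is 0.258 (0.059 to 1.12) against 0.279 (0.064 to 1.21).

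**The case against.** **The gap may be zero.** Total study follow-up has no stated start. If analysts used the Protocol 9 definition of enrolment, or read Protocol 5 literally, no pre-dose time would exist. Protocol 6.1 also ties the first two years of visits to the first dose. The nearest SAP statement of a start at enrolment, in 7.2, concerns the treatment summary and not the infection denominator. The person-time example that SAP 6.6 refers to is not visible in the text available and might settle the matter. This stands as a condition on the pre-dose half of the point. It does not help patients who started treatment before enrolment.

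**The intended meaning is stated.** The scope sentence, the explicit formula and SAP 5.3.1 all exclude pre-dose time. That is true, but the sentence declared to govern the analysis is the subtraction.

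**Events before the first dose can be captured.** A reader might infer that the interval has no possible numerator, because Protocol 9 starts recording after a dose. The documents do not support that. The flowchart note in the protocol has patients asked about events since the last evaluation, and Protocol 9.2 gives the reporting period from enrolment without the dose condition. What remains is that such an event has no exposure class.

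**The comparator is partly a label.** Protocol 7.4 compares with time without use of etanercept, which could include pre-dose time. The conflict is with the SAP's definition of past exposure.

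**The effect is small.** At 5 infections per group the 95% interval spans about 19-fold (35.5/1.88), and the registry is descriptive with no hypothesis test. This stands, and it limits the weight of the point.

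**Conclusion.** The point holds as a defect in a stated rule. The subtraction in SAP 6.6 contradicts the scope of its own bullet and, where follow-up starts before the first dose, SAP 5.3.1. It gives wrong past time whenever follow-up starts on a date other than that of the first dose.

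A reader might conclude that the rate ratio is biased upward. The documents do not support that, because the same rule understates past time for patients already on treatment, whom Protocol 4.2 admits whatever their prior duration. Protocol 6.2 expects few of them, but gives no number. The net direction is therefore unknown.

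The pre-dose error is about 1% to 8% of the rate ratio with 40 patients waiting 2 to 8 weeks and 80 to 150 patient-years of past time. It reaches 29% per patient with 1,400 days of treatment and a 90-day gap. All of these gaps, patient numbers and past-time totals are assumptions. The error is modest beside the expected imprecision, but it can be removed by definition.

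**What to change.** 1. Reconcile the enrolment date across Protocol 5, Protocol 9, SAP 5.3.1 and SAP 6.5, so that one definition serves reporting and analysis.
2. In SAP 6.6, start infection and SAE person-time at the later of enrolment and first dose, and end it at the end of follow-up.
3. Truncate current/recent time (each treatment period plus 28 days) to that window. Without this step, already-treated patients remain miscounted.
4. Define past time as the remainder of the window. This replaces both the subtraction from total follow-up and the explicit formula. Reverting to the explicit formula alone is not enough: it overlaps by one day, and by a further 28 days per gap if the whole dose-free interval between courses is counted.
5. Restrict event counts to the same window, and list events between consent and first dose separately as pre-treatment.

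The cost is a few sentences in the SAP, an aligned definition in the protocol and a small programming change. Consent and first-dose dates are already collected at baseline (Protocol 6.2.1). Total person-time and some event counts may change slightly, so the report should state the window used.

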## 7. Primary and Secondary Analyses

Evaluations and interpretations will be based on point estimates and 95% confidence intervals (CI) as evaluation of the statistical precision around the point estimate, unless otherwise specified. No formal hypothesis testing is planned. This approach follows the *Guidelines for Good Pharmacoepidemiology Practices*, Section D, point 10 [1]. Unless otherwise specified, all listings and tables are based on the total Registry population at the time of data cut-off for analysis.

### 7.1 Summary of baseline characteristics and demography

For enrolled patients, line listings for all baseline characteristics (including medical history) and demography data will be generated.

The following tabular summaries will be generated:

- Demography (age at enrollment, gender, race/ethnicity)
- Plaque psoriasis status (duration of disease, baseline severity, presence of psoriatic arthritis, age at diagnosis of plaque psoriasis)
- Previous/current plaque psoriasis therapies (proportion of patients with previous/current use of topical steroids, methotrexate, cyclophosphamide, etc)

Demography summary will also be generated by gender as per basic result disclosure (Pfizer standard).

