7.3. Baseline Assessment

The demographic and clinical profile of the registry population will be described using baseline data. Patient demographics, psoriasis severity, history of psoriasis and psoriasis treatment(s) prior to first etanercept administration will be summarized. Data will be

summarized overall and by status at enrolment to explore whether the patients treated prior to registry enrolment are different than the overall population.

Continuous variables (e.g., age) will be reported as means and standard deviations. Categorical variables (e.g., gender) will be summarized as number and percentage (%) of the total registry population.

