#### **6.6 Derivations**

The following derived/calculated values will be used:

[figure not shown]
- Age at enrollment in years:  $[\text{date of enrollment} - \text{date of birth} + 1] / 365.25$
- Duration of disease at enrollment in years:  $[\text{date of enrollment} - \text{date of diagnosis} + 1] / 365.25$
- Cumulative exposure in weeks by the duration of chronic exposure for each period of etanercept exposure:  $[(\text{last dose date} - \text{first dose date} + 1) + 28] / 7$ . A treatment period is defined as continuous treatment with no interruptions of more than 28 days. Restarting treatment within 28 days is considered as having continuous exposure
- Duration of each etanercept treatment period (in weeks):  $(\text{last dose date} - \text{first dose date} + 1) / 7$
- Time at risk of malignancy (in years):  $[\text{date of malignancy diagnosis or end of follow-up if no malignancy is found} - \text{initial treatment dose date} + 1] / 365.25$

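### Age and disease duration are derived only at enrolment, so the planned comparison of already-treated patients carries a treatment-lag artefact; add first-dose values

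*SAP*

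**What the plan says.** SAP 6.6 defines "Age at enrollment in years" and "Duration of disease at enrollment in years", both from the enrolment date. SAP 7.1 tabulates "Demography (age at enrollment, gender, race/ethnicity", disease duration, "age at diagnosis of plaque psoriasis", and "Previous/current plaque psoriasis therapies (proportion of patients with previous/current use of topical steroids" and other agents. Neither section derives age or duration at first dose. SAP 5.4 lists these variables as collected at baseline, which SAP 5.1 places at enrolment.

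Protocol 7.3 says that "psoriasis treatment(s) prior to first etanercept administration will be summarized", and that the data are to be "summarized overall and by status at enrolment to explore whether the patients treated prior to registry enrolment are different than the overall population". Protocol 4.2 admits patients "actively being treated with etanercept, regardless of length of treatment prior to study enrolment", and it sets the age limit at the first dose. Protocol 6.2.1 collects the first-dose date.

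SAP 6.5 classes a patient as prospective if etanercept began no more than 30 days before enrolment, or after it; all others are retrospective. SAP 7.1 does not itself call for a split by enrolment type, but the SAP's document history records a retrospective-patient column added to three table series.

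**The concern.** The two groups are measured at different points in their treatment. A prospective patient's age and disease duration are taken close to the first dose. An already-treated patient's are taken after whatever time has passed since the first dose, with no upper limit. The comparison in Protocol 7.3 is meant to show whether already-treated enrolees are a different kind of patient. An excess in age or disease duration that comes only from the reference date could be read as a real difference, or could hide a real one in the opposite direction.

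The same question arises for therapies. The protocol ties the treatment summary to the period before the first dose, while the SAP's wording covers current use as well. For a patient already on etanercept, a therapy current at enrolment may have been started after the first dose.

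**Working it through.** The documents state no figure for this comparison, so there is none to reproduce.

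**Inputs from the documents**
- Reference date for age and duration: enrolment (SAP 6.6).
- Lag in already-treated patients: no limit (Protocol 4.2).
- Lag in prospective patients: at most 30 days, or 30/365.25 = 0.082 y; it may be zero or negative (SAP 6.5).
- Comparator: the overall population (Protocol 7.3).
- Recruitment target: 60 to 80 (Protocol 3, SAP 4).

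**Assumed, because not given**
- Mean lag in already-treated patients: 0.25 to 3 y.
- Already-treated share f: 0.10 to 0.50. Protocol 6.2 says only that few such patients are expected.
- SD of age: 2.5 to 3.5 y.

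Lags near two years are possible. From the authorisation of 22 December 2008 (Protocol 1.1) to the planned first enrolment in Q4 2010 (Protocol 5) is 1.77 to 2.02 y.

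**Step 1: the identity.** Value at enrolment = value at first dose + lag. To illustrate with an invented record: born 1 Jan 1998, diagnosed 1 Jan 2007, first dose 1 Jun 2011. Enrolled on the day of first dose, the SAP 6.6 formulas give age 4900/365.25 = 13.42 y and duration 1613/365.25 = 4.42 y. Enrolled on 1 Jun 2013 while still treated, they give 15.42 y and 6.42 y.

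**Step 2: against prospective patients.** If the groups are identical at first dose:

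retrospective mean − prospective mean = mean lag (R) − mean lag (P).

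**Step 3: against the overall population.** Overall mean = f × R + (1 − f) × P, so:

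retrospective mean − overall mean = (1 − f) × [mean lag (R) − mean lag (P)].

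**Step 4: results in years**, for age and for disease duration alike. The second column runs from a mean prospective lag of 30 days to one of zero; the last three take it as zero.

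| Assumed mean lag (R) | vs prospective | vs overall, f = 0.10 | f = 0.25 | f = 0.50 |
|---|---|---|---|---|
| 0.25 | 0.17 to 0.25 | 0.225 | 0.188 | 0.125 |
| 0.5 | 0.42 to 0.50 | 0.45 | 0.375 | 0.25 |
| 1 | 0.92 to 1.00 | 0.90 | 0.75 | 0.50 |
| 2 | 1.92 to 2.00 | 1.80 | 1.50 | 1.00 |
| 3 | 2.92 to 3.00 | 2.70 | 2.25 | 1.50 |

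A simulation of 400,000 patients, with the same age distribution at first dose in both groups and prospective lags uniform on ±30 days, agreed within random error. For a 1-year lag it gave 0.987 to 0.998 y against prospective patients, and 0.888, 0.749 and 0.498 y against overall.

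**Step 5: scale against noise.** The 95% half-width of a retrospective-minus-prospective difference in mean age is 1.96 × SD × √[1/(Nf) + 1/(N(1 − f))].
- Smallest (SD 2.5, N = 80, f = 0.50): 1.96 × 2.5 × √(1/40 + 1/40) = 1.10 y.
- Largest (SD 3.5, N = 60, f = 0.10): 1.96 × 3.5 × √(1/6 + 1/54) = 2.95 y.

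A lag of a few months would be lost; a lag of two years or more could show.

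**Step 6: after the change.** With both variables taken at first dose, the lag drops out. Both differences are zero for groups identical at first dose, whatever the lag or f.

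**The case against.** The strongest reply is that the enrolment anchor is ordinary baseline description. The protocol's flowchart equates enrolment with baseline, Protocol 6.2.1 collects age at that visit, and the primary analyses cover events during registry participation. In Protocol 7.3 the reference to first administration most naturally attaches to the treatments, not to age or duration. This stands: age at enrolment is a legitimate variable, and a reader who infers that tabulating it breaches the protocol goes too far. Likewise, a patient first dosed at 17 who appears as an adult at enrolment is correctly described.

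It can also be said that the effect is small and partly visible. No hypothesis test is planned, few already-treated patients are expected, and short lags would vanish in noise. Age at diagnosis, gender and race/ethnicity do not depend on the lag, and the patient listings show exposure dates. All of this is true and limits the point. But descriptive tables are read directly, and nothing in the summary separates a longer disease course before etanercept from time already spent since starting it.

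On therapies, Protocol 6.2.1 records prior treatments separately from systemic therapies added since starting etanercept. It therefore cannot be said that the SAP table does count later therapies. The wording allows it, and the table shells were not available to check.

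**Conclusion.** The point holds as a modest, inexpensive improvement. For groups identical at first dose, the SAP's derivations produce an excess in mean age and disease duration in already-treated patients. With an assumed 1-year mean lag this is about 0.9 to 1.0 y against prospective patients and 0.5 to 0.9 y against overall (f from 0.50 to 0.10). The direction, for lags longer than those of prospective patients, follows from the definitions. The size rests on assumed values of the lag and f.

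Three stronger readings are tempting and not supported. A reader might infer that the protocol's comparison shows a difference equal to the full lag. It does not, because the overall population contains the already-treated patients, and even against prospective patients it is a difference between two mean lags. A reader might infer that the safety results are biased. No incidence rate, rate ratio or SIR in the SAP is built on these two baseline summaries. Finally, a reader might expect re-anchoring to expose the depletion of susceptible patients discussed in Protocol 7.6. It cannot, because patients who stopped for good before their site joined are not in the registry.

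**What to change.** In SAP 6.6, add age at first dose, (first-dose date − birth date + 1)/365.25; disease duration at first dose, (first-dose date − diagnosis date + 1)/365.25; and the lag from first dose to enrolment. In SAP 7.1, present all three by enrolment type and overall, and base the prospective/retrospective comparison on the first-dose values. Keep the enrolment values as description. Define the prior-therapy summary as therapies started before the first dose, in line with Protocol 7.3, and show later or current therapies separately if they are wanted.

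The first-dose date is already collected, so age, duration and lag need no new data item. The cost is SAP wording, three derived variables and a slightly longer table.
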